7.D. Sample Size Justification. The power of this trial was evaluated based on the difference in the primary outcome, mean uw-mRS at 90 days. Based on preliminary data, we expected that 1.8 times as many MSU patients will be enrolled than SM patients due to a greater propensity of first responders to alert the MSU team on MSU weeks compared to SM weeks. With a sample size of **693 total tPA-eligible patients** (446 MSU and 247 SM patients, assuming 10% lost to follow-up), the study will have 80% power with a 0.05 Type I error rate to detect a difference between groups of 0.09 in the mean Δ uw-mRS using a two-sample t-test. This difference is plausible and important. In 90 patients randomized in our pilot study comparing a combination of Argatroban + tPA to standard tPA treatment, 90 d mean+s.d. uw-mRS was 0.59+ 0.35 with the combination vs 0.49+ 0.37 with tPA alone (a difference of 0.1), slightly greater than the difference we project. In a re-analysis of 11 other acute stroke studies, the difference in mean 90d uw-mRS between groups ranged from 0.024-0.25, with most trials in the range of 0.1. We initially based our effect size on the NINDS tPA trial. In that study, 90d mean uw-mRS was 0.09 (0.59 vs 0.50) with tPA vs placebo; tPA was considered a "breakthrough" therapy based on this result. A sample size of 563 and 878 would be needed to detect a difference of 0.1 and 0.08 respectively.

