7.I.3.b. Survival and Healthcare Utilization Analyses. Survival will be analyzed using Cox proportional hazards models, adjusting for baseline covariates NIHSS, age, pre-morbid mRS, and previous TIA/stroke. We will also adjust for any additional baseline covariates that are imbalanced between treatment groups. If there are too many covariates to include in the model we will use a prescreening approach, testing covariates at the 0.20 level and including those that meet the latter criteria for significance. We will use both graphical methods⁵³ and statistical tests to check the proportional hazards assumption of the Cox regression model.

We will first use the graphic methods for detecting violations of the proportional hazards assumption. The plot of survival curves are based on the Cox Model and Kaplan-Meier estimates for each subgroup decided by covariates. Clear departures of two estimates indicate evidence against the assumption of proportional hazards. Another plot to be used is the plot of difference of the log cumulative baseline hazards versus time. Under proportional hazards, this plot is constant over time and centered on the estimated log-hazard ratio. Any time trend of the difference will suggest the violation of the proportionality assumption. Note that both plots only inform us if baseline hazards are proportional or not, and do not give detailed information about the type of departure from the proportionality. The plot of martingale residuals could be applied to determine the functional form to be used for a given covariate to best explain its effect on survival through a Cox proportional hazards model. The best functional form could be a transformation of the covariates (Z), such as log Z, or it may be a discretized version of the covariate. Under this situation, the martingale residuals are useful for determining cut points for the covariates. For example, we assume that Z1 is a single covariate of the covariate vector Z for which we are unsure of what functional form of Z1 to use. Let f(Z1) be the best function of the covariate Z1 to explain on survival. To find the form of the function f, we will fit the data based on Z and compute the martingale residuals. Then we plot these residuals against the values of Z1. The smoothed-fitted curve then gives an indication of the best function. For example, if the plot is linear, no transformation of Z1 is needed. If the plot is a piece-wise constant, then a discretized version of Z1 is suggested.

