5.1.2. Primary Clinical Analysis

The mean uw-mRS at 90d along with corresponding two-sided 95% confidence intervals will be compared between groups using a two-sample t-test or Wilcoxon rank sum test if the assumption of normality does not hold. Although the mRS is an ordinal outcome, the difference between the uw-mRS categories has clinical significance and the t-test assumption and central limit theorem are likely satisfied. The primary analysis of uw-mRS will be adjusted for baseline uw-mRS, site, any baseline covariates that are different between the two groups, and covariates associated with mRS, including baseline NIHSS, age, pre-morbid mRS, and previous TIA/stroke, in a linear regression model. If the assumptions of the model are not satisfied, a restricted cubic spline will be used to model baseline continuous variables (NIHSS and age). If the linear regression with splines does not fit well, we will use ordinal logistic regression to adjust for the variables. If the proportional odds assumption fails, we will use logistic regression with mRS 0-1 vs 2-6 as the primary analysis. Assuming that the primary analysis doesn't use the following models, sensitivity analyses of the primary outcome will be conducted including ordinal (shift) analysis using a proportional odds model and proportion achieving a dichotomized outcome of mRS 0-1 vs 2-6 using binary logistic regression.

In response to peer review, we added post-hoc propensity score analyses using propensity scores as an alternative way to reduce any effects of confounding to estimate the effect of MSU group on dichotomized mRS (0-1 versus 2-6). The individual propensities for enrolling into the MSU versus EMS groups were estimated using a separate selection multivariable logistic regression model with variables site, baseline NIHSS, pre-stroke

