5.1.4. Analyses of Ancillary Clinical Outcomes

We will also compare mRS at 90d (uw-mRS, Δ uw-mRS from baseline, ordinal (shift) analysis, and proportion achieving 0,1) in tPA treated patients treated within 60 minutes of LSN to patients treated 61-270 minutes, regardless of whether they were on MSU weeks vs. SM weeks. Patients on MSU weeks vs SM weeks will also be compared for differences in (a) the time from LSN to tPA treatment, (b) time from LSN, alarm time, and ED arrival to start of IAT, and for safety outcomes (i) mortality, (ii) symptomatic intracerebral hemorrhage, and (iii) incidence of tPA treated stroke mimics and transient ischemic attacks.

A logistic regression model will be used to compare 90 day mRS 0,1 vs 2-6 of patients treated with tPA within 60 minutes of symptom onset to similar patients treated 61-270 minutes after onset, adjusting for any imbalances in stroke severity (baseline NIHSS, age, premorbid mRS, and previous stroke/TIA incidence) between the groups at the time of treatment⁸. If baseline characteristics are significantly different between the two non-randomized groups, we will use propensity score analysis to limit potential bias. Also, we expect a higher incidence of spontaneous recovery (TIA) and stroke mimics may occur with earlier observation in the 0-60 minute group compared to those seen 61-270 minutes. The “natural history” of the incidence of spontaneous recovery and stroke mimics will be estimated from patients enrolled into the SM group, and will be considered in analyzing the comparison between patients treated with tPA within 0-60 min vs 61-270 min. Time to treatment and to endovascular procedures will be analyzed using Cox proportional hazards models, similarly to survival. Categorical outcomes will be analyzed using Fisher’s exact test.

Unless there is sufficient power (predetermined before the analysis is begun) the approach to ancillary analysis will generally be the calculation of confidence limits on intervention group differences rather than formal tests of significance as the trial may not have high power to detect difference in all of these outcomes. However, these comparisons will add to the knowledge of the benefits and risks of the intervention.

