6.2. Interim Analyses for Effectiveness

The efficacy interim analysis of the 90 day dichotomized mRS will be a 2-sample, 2-sided test of proportions using a Haybittle-Peto boundary ($p=0.001$). This will be conducted on the subset that are tPA-eligible based on the blinded adjudication.

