6.3. Interim Analyses for Futility

The futility analysis of the 90 day dichotomized mRS (0-1 vs 2-6) will be a 2-sample, 1-sided, test of proportions. The futility analysis will compare patients in MSU weeks vs SM weeks ($\alpha=0.15$). If we reject the null hypothesis that the percentage of favorable outcomes ($mRS < 2$) in patients in the MSU weeks is greater than or equal to the percentage of favorable outcomes in patients in the SM weeks plus 10%, we conclude that completing the trial would likely be futile. The futility hypotheses are: $H_0: p_{MSU} - p_{SM} \geq \Delta$ versus $H_A: p_{MSU} - p_{SM} < \Delta$ where p_{MSU} and p_{SM} are the proportions of participants expected to have a favorable mRS outcome in the MSU and SM groups, respectively, and Δ denotes the 10% increase in favorable outcomes over SM considered clinically meaningful. This will be conducted on the subset that are tPA-eligible based on the blinded adjudication.

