6.5. Process Analysis

Time from alarm to treatment decision will be compared using a one-sided Wilcoxon rank sum test ($\alpha=0.05$) to test if the time is longer for the MSU arm. This will be conducted on the subset that are tPA-eligible based on the blinded adjudication. MSU-by-site interaction terms will be included in a regression model to test if these differ by site and if the interactions are

significant then within-site tests will be conducted.

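### Site is in the primary model but is not named for the secondary time and categorical analyses or for the interim efficacy, futility, sICH and lead process tests, so unequal MSU:SM ratios across sites could bias them modestly

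*SAP*

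**What the plan says.** Protocol 4.E has each added site commit to randomized MSU and SM weeks. Protocol 5.C.1 adds that some sites run two locations that take opposite arms in the same week. SAP 5.1.2 puts site in the primary model: "The primary analysis of uw-mRS will be adjusted for baseline uw-mRS, site".

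For the other comparisons:

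- **Secondary times (SAP 5.1.4):** "Time to treatment and to endovascular procedures will be analyzed using Cox proportional hazards models, similarly to survival". No site term or stratum is named.
- **Categorical outcomes (SAP 5.1.4):** "Categorical outcomes will be analyzed using" Fisher's exact test.
- **Interim efficacy (SAP 6.2):** the test "will be a 2-sample, 2-sided test of proportions using a Haybittle-Peto boundary".
- **Interim futility (SAP 6.3):** the test "will be a 2-sample, 1-sided, test of proportions", with a 10-point margin and alpha 0.15.
- **Interim symptomatic hemorrhage (SAP 6.4):** Fisher's exact test.
- **Interim process (SAP 6.5):** "Time from alarm to treatment decision will be compared using a one-sided Wilcoxon rank sum test". A regression with MSU-by-site interaction terms follows, with within-site tests if the interactions are significant.
- **Survival (Protocol 7.I.3.b):** a Cox model "adjusting for baseline covariates NIHSS, age, pre-morbid mRS, and previous TIA/stroke", plus any further baseline covariate that is imbalanced. Site is not listed.

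On the ratio, Protocol 7.D says that preliminary data led the team to expect that "1.8 times as many MSU patients will be enrolled than SM patients". SAP 4.1 explains that SM-week patients had been lost to non-participating hospitals and that this gap has been mitigated. It then plans on 3:2 overall.

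**The concern.** Assignment happens within site, so the natural comparison is also within site. A pooled test compares all MSU patients with all SM patients. If one site supplies a larger share of the MSU arm than of the SM arm, and that site has slower times or worse outcomes for local reasons, part of the site difference appears as an MSU effect or hides one.

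Both conditions are plausible here. The early 1.8:1 expectation arose from local hospital arrangements. SM enrolment during MSU weeks needs a second SM team covering the area (Protocol 5.C.3, SAP 3.1), which can shift the ratio at some sites only. Protocol 1.B expects traffic, distances and local EMS and ED rules to affect implementation, and SAP 5.1.5 expects demographic differences between telemedicine and on-board-neurologist sites.

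Most is at stake in the futility rule, because a wrong stop cannot be undone. The secondary claims come next: a site-adjusted primary result and unadjusted secondary results could disagree for no clinical reason.

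This is about site as the stratum of assignment, not about correlation within deployment weeks.

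**Working it through.** **The plan's own figure.** SAP 4.1 gives N = 1038 for a difference of 0.07, SD 0.385, ratio 1.5 and 5% loss; alpha 0.05 and 80% power are carried over from the earlier calculation in the same section.

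n(SM) = (1 + 1/1.5) × (1.960 + 0.842)² × (0.385/0.07)² = 1.667 × 7.849 × 30.25 ≈ 396

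n(MSU) = 1.5 × 396 = 594, so 990 are evaluable. Dividing by 0.95 gives 1043; multiplying by 1.05 gives 1040. The stated 1038 reproduces to within 0.5%. Site plays no part in it, so this point leaves it unchanged.

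**Inputs for the site question.**
- Interim N: 0.5 × 1038 = 519 (SAP 6.1).
- Houston share: 150 + 3 × 90 = 420 of 1038, about 40% (Protocol 5.J).
- Assumed: Houston 1.8:1 and other sites 1.3:1. No document gives a ratio by site.

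**Does this fit the planned ratio?** MSU share = 0.4 × 1.8/2.8 + 0.6 × 1.3/2.3 = 0.257 + 0.339 = 0.596, or 1.48:1. It does.

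**Bias of a pooled difference.** Houston makes up 0.257/0.596 = 43.1% of the MSU arm and 0.143/0.404 = 35.4% of the SM arm. If Houston's outcome differs by g, the pooled difference is off by g × (0.431 − 0.354) = 0.077g.

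**Futility test, true gain exactly 10 points.** Assume mRS 0-1 near 55% (MSU) and 45% (SM), with arms of about 309.5 and 209.5.

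SE = √[0.2475 × (1/309.5 + 1/209.5)] ≈ 0.0445

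P(stop) = Φ(−1.036 − bias/SE)

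| Houston rate vs other sites | Bias (points) | P(stop), nominal 15% |
|---|---|---|
| 5 points lower | −0.39 | 17% |
| 10 points lower | −0.77 | 19% |
| 15 points lower | −1.16 | 22% |
| 5, 10, 15 points higher | +0.39, +0.77, +1.16 | 13%, 11%, 10% |

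**Other tests, same site mix, no MSU effect (simulation).**

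| Test | Assumed site difference | Pooled rejection, nominal 5% |
|---|---|---|
| Cox, N = 1038 | site hazard ratio 1.25, 1.5, 2.0 | about 6%, 7%, 10% |
| Fisher, N = 1038 | 25%, 30%, 35% vs 15% | about 6%, 7%, 7% |
| Process Wilcoxon (one-sided), N = 519 | Houston slower by 0.25, 0.5, 0.75 SD | about 8%, 11-12%, 14-16% |

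Site-stratified versions stay near 5% (futility near 15%). Simulation error is about one point: 1.96 × √(0.07 × 0.93/2000) = 0.011. The upper-end values could therefore be a point or so higher.

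**Sensitivity.** If the 1.8:1 stratum held 56% of patients and the rest ran at 1.2:1 (1.5:1 overall), null rejection for Cox would be 8% at a site hazard ratio of 1.5 and 18% at 2.0. Futility stopping with a 10-point gap would be 21% or 10%, depending on direction.

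**Interim efficacy.** Null rejection at the 0.001 boundary is 0.0013 to 0.0033 across strata ratios of 1.8:1 against 1.0-1.2:1 and site gaps of 10 to 20 points.

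**Equal ratios at every site.** Bias is zero under no effect, and futility stopping is 15.0%. About 5 points of power are lost at a 0.75 SD site difference. A true Cox hazard ratio of 1.5 is estimated at 1.44 to 1.47 without site.

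**The case against.** The case on the other side has real substance.

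- **Process analysis.** A reader might infer that every interim decision ignores site. SAP 6.5 does not support that, because it adds an MSU-by-site regression. That step looks for an MSU effect that differs by site, however. Confounding by site needs no such difference, and the lead Wilcoxon test stays pooled.
- **Survival and times.** A reader might take the survival model for a bare pooled test. It is covariate-adjusted and admits imbalanced baseline variables, and the times are to be analyzed like survival. SAP 5.1.1 has a parallel rule for secondary adjusted analyses. At 1.8:1 against 1.3:1 and N = 1038, a 5% test would flag site as imbalanced about 70% of the time. But neither document says that site counts as a baseline covariate, and neither rule reaches the interim tests.
- **Size.** A reader might expect error rates near 30%. Setting other sites at 1:1 does give up to 26% for Cox and 29% for the process test. That mix, however, is 1.26:1 overall, not the planned 1.5:1, and holding Houston at 1.8:1 throughout sits badly with SAP 4.1, which says the groups are now balanced.
- **Process false alarms.** They assume that the MSU saves no time. Even with other sites at 1:1, they fall to 1%, 3% and 6% if the MSU is 0.1 SD faster, and to about zero at 0.25 SD.
- **Existing checks.** Site is a pre-specified subgroup (SAP 5.1.5) and is in the post hoc propensity model (SAP 5.1.2). Ancillary results are mostly to be confidence limits. These help, but a pooled interval carries the same bias, and a post hoc analysis cannot protect an interim decision.

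**Conclusion.** The point holds in a limited form. The plan adjusts for site in the primary model but names no site term for the secondary time and categorical analyses, for the interim efficacy, futility and symptomatic-hemorrhage tests, or for the lead process test. Site enters the survival model only if it is treated as an imbalanced baseline covariate.

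Under a site mix that matches the planned ratio, the distortion is modest, with futility most important. The process figures apply only if the MSU saves no time, and the effect on interim efficacy is negligible in absolute terms.

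All of this needs both unequal ratios and site differences in outcome. The documents make these plausible but do not quantify them, so they do not show that any result is in fact biased. Nor do they support adding location strata to the primary model, for which there is no supporting calculation. This is worth changing because the repair is cheap, not because a large error has been shown.

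**What to change.** State the site-stratified form of each test:

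- **SAP 6.3 and 6.2:** a site-stratified risk difference, keeping the 10-point margin and alpha for futility; Cochran-Mantel-Haenszel is an alternative for efficacy. Futility comes first.
- **SAP 6.5:** the van Elteren test in place of the pooled Wilcoxon, keeping the interaction regression.
- **SAP 5.1.4 and Protocol 7.I.3.b:** Cox models stratified by site for time to tPA, time to IAT and survival.
- **SAP 5.1.4 and 6.4:** Cochran-Mantel-Haenszel for categorical outcomes, or an exact stratified test for sparse events such as symptomatic hemorrhage.
- **Small sites:** name in advance a rule that pools very small sites into one stratum for sparse events.

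The cost is SAP wording, slightly more analysis work and a variable already needed for the primary model. The downside is sparse strata: new sites were projected at 1 to 2 tPA-eligible patients per month (Protocol enrollment projections), and about 17% of MSU tPA-treated patients had received IAT (Protocol 5.I). Where a pooled result has already been reported, the stratified result can be shown beside it and labelled post hoc.

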5.1.5. Subgroup Analysis

Tests of effects within subgroups will be driven by clinical rationale. To reduce the potential for spurious results, we would test for a sub-group treatment interaction at a 0.2 critical level. Any subgroup analyses that are not pre-specified would be considered post hoc and reported as requiring confirmation in future studies. Estimates of the MSU effect will be obtained separately for pre-specified subgroups with significant treatment-by-subgroup interactions, using the methods described above. Pre-specified subgroups include (1) patients treated via TM versus on-site VN, (2) patients treated at various sites, (3) patients that had the EMS arrive (for SM) or MSU arrive (for MSU) within ≤ 1 hr and those that arrived >1 hr of LSN, and (4) race. For (3), time will also be considered as a continuous variable and the interaction between time and MSU/SM will be assessed with transformations or restricted cubic splines of time used if appropriate).

When doing the TM subgroup analysis, we anticipate that there may be demographic differences between sites that are doing TM versus onboard VN. For this analysis we will conduct regression models, adjusting for baseline NIHSS, age, pre-morbid mRS, time since last seen normal, and previous TIA/stroke, in a linear regression model.

Analyses of post-randomization sub-groups are subject to many biases. Thus any analyses of post-randomization sub-groups, such as those treated with IAT, would be considered on a case by case basis requiring tailored use of advanced statistical methods⁹ and careful interpretation.

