Rates of symptomatic hemorrhage will be compared using a Fisher's exact test (alpha=0.05). The futility analysis of the 90 day dichotomized mRS (0-1 vs 2-6) will be a 2-sample, 1-sided, test of proportions. The futility analysis will compare patients in MSU vs SM weeks (alpha=0.15). If we reject the null hypothesis that the percentage of favorable outcomes (mRS<2) in MSU patients is greater than or equal to the percentage of favorable outcomes in SM patients plus 10%, we conclude that completing the trial would likely be futile. The futility hypotheses are: $H_0: p_{MSU} - p_{SM} \ge \Delta$ versus $H_A: p_{MSU} - p_{SM} \le \Delta$ where p_{MSU} and p_{SM} are the proportions of participants expected to have a favorable mRS outcome in the MSU and SM groups, respectively, and Δ denotes the 10% increase in favorable outcomes over SM considered clinically meaningful. The efficacy interim analysis of the 90 day dichotomized mRS will be a 2-sample, 2-sided test of proportions and will be monitored using an O'Brien-Fleming boundary with Lan-DeMets alpha spending function 35,36 . Time from alarm to treatment decision will be compared using a one-sided Wilcoxon rank sum test (alpha=0.05) to test if the time is longer for the MSU arm.

7.F. Heterogeneity of Treatment Effects. Tests of effects within subgroups will be driven by clinical rationale. To reduce the potential for spurious results, we would test for a sub-group treatment interaction at a 0.2 critical level. Any subgroup analyses that are not pre-specified would be considered post hoc and reported as requiring confirmation in future studies. Estimates of the MSU effect will be obtained separately for pre-specified subgroups with significant treatment-by-subgroup interactions, using the methods described above. Pre-specified subgroups include (1) patients treated via TM versus on-site VN, and (2) patients treated at various sites.

Analyses of post-randomization sub-groups are subject to many biases. Thus any analyses of post-randomization sub-groups, such as those treated with IAT, would be considered on a case by case basis requiring tailored use of advanced statistical methods³⁷ and careful interpretation.

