3.3. Multiplicity

No adjustments for multiple comparisons will be made. However, the secondary analyses will be interpreted with caution.

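### Separate subgroup estimates of the MSU effect are planned only where an interaction passes at 0.2, so the estimates produced are selected for looking different; all pre-specified subgroups should be reported.

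*SAP*

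**What the plan says.** SAP 5.1.5 gives both the test level and its reason: "To reduce the potential for spurious results, we would test for a sub-group treatment interaction at a 0.2 critical level". The reporting rule follows: "Estimates of the MSU effect will be obtained separately for pre-specified subgroups with significant treatment-by-subgroup interactions". Protocol 7.F carries the same level ("we would test for a sub-group treatment interaction at a 0.2 critical level") and the same reporting rule.

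The SAP names four factors. The first two are also in the Protocol: "Pre-specified subgroups include (1) patients treated via TM versus on-site VN, (2) patients treated at various sites". The SAP adds arrival within one hour of last seen normal versus later, and race. It also plans a further test on arrival time: "For (3), time will also be considered as a continuous variable and the interaction between time and MSU/SM will be assessed".

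On multiplicity, SAP 3.3 says: "No adjustments for multiple comparisons will be made. However, the secondary analyses will be interpreted with caution". The only subgroup-specific caveat is for analyses outside the list: "Any subgroup analyses that are not pre-specified would be considered post hoc and reported as requiring confirmation in future studies".

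**The concern.** The gate decides which subgroup effects are estimated separately. Because it opens only when the effects look different, the estimates it produces are a selected set, and under chance variation they overstate the difference. Where the MSU effect is consistent, no separate estimates are planned.

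That works against the trial's own purposes. The Protocol synopsis wants to confirm that a remote vascular neurologist can replace one on board. Protocol 5.C.3 promises to examine remote versus on-site assessment, and Protocol 5.J adds sites partly for generalizability. These aims need effects by TM status and by site with confidence intervals, most of all when the effects agree.

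The label matters too. A pre-specified interaction with p = 0.19 would be called significant and would not carry the confirmation caveat that an unlisted subgroup would. At stake is how results by site, TM, arrival time and race are read. The primary comparison is not affected.

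**Working it through.** **The plan's own figures.** The 0.2 level is a design choice, and the documents give no false-positive rate for the subgroup plan, so there is nothing to reproduce there. The design inputs used below do reproduce. SAP 4.1 gives a difference of 0.07, SD 0.385, a 3:2 ratio and 5% loss. The two-sided 0.05 level and 80% power are stated for the initial sample size of 693 and assumed unchanged.

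- SM arm: (1 + 1/1.5) × (1.960 + 0.842)² × (0.385/0.07)² ≈ 396. MSU arm: 1.5 × 396 = 594. Total 990.
- Inflated for loss: 990/0.95 ≈ 1043, or 990 × 1.05 ≈ 1040. The plan has 1038.

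**Chance that at least one interaction passes, with no true heterogeneity.** For k independent tests at 0.2 this is 1 − 0.8^k.

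| Tests counted | At 0.2 | At 0.05 |
|---|---|---|
| 2 (Protocol list) | 36.0% | 9.8% |
| 3 (SAP list without TM) | 48.8% | 14.3% |
| 4 (SAP list) | 59.0% | 18.5% |
| 5 (SAP list plus continuous time) | 67.2% | 22.6% |

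**Allowing for overlap between tests.** With four equally correlated normal statistics the chance is 56% at correlation 0.3, 51% at 0.5 and 48% at 0.6. A simulation closer to the trial used 986 patients, seven sites, 60% on MSU, TM assigned by site, a race mix that varied by site, and no MSU effect anywhere. That structure is assumed, not taken from the documents. It gave:

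- 56-57% for the four SAP factors, and 61-62% with continuous time;
- 48-49% without TM, and 54-55% without TM but with continuous time.

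The runs without TM matter because Protocol 5.C.4 says TM is not used on SM weeks, so SM patients have no TM status of their own.

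**Size of the selected differences.** Evaluable patients: 1038 × 0.95 ≈ 986, or about 394 SM and 592 MSU.

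- SE of the overall effect: 0.385 × √(1/394.4 + 1/591.7) = 0.0250.
- SE of the difference between two equal subgroups: 2 × 0.0250 = 0.050.
- A difference passes at 0.2 once it exceeds 1.282 × 0.050 = 0.064.
- Mean absolute difference among chance findings that pass: 0.050 × φ(1.282)/0.10 = 0.050 × 1.755 = 0.088.

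**What the gate does well.** Assume a uniform effect of 0.07 and an even split. One subgroup is then significant at 0.05 and the other is not in 50% of trials without a gate, 18% with a gate at 0.2 and 5% with a gate at 0.05.

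**Power for a true interaction of 0.07, even split.** The standardized difference is 0.07/0.050 = 1.40. Power is 55% at 0.2 and 29% at 0.05.

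**The case against.** The best defence is that the stated reason is sound when read in order. SAP 5.1.5 opens with tests within subgroups and then introduces the interaction test as a check on them. Against ungated tests, a gate at 0.2 does cut spurious contrasts, from 50% to 18% in the example. A reader might infer that 0.2 works against the stated aim; that follows only if the comparison is with 0.05, and the text does not make that comparison. This part of the defence stands.

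It also stands that 0.2 can be defended as a sensitive screen, since a 0.05 cut would miss about 71% of true interactions as large as the design effect. The SAP does not give that reason, however, and a screen should not decide which estimates are produced.

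A reader might also infer that consistent subgroups will never be shown. The text does not say so. It plans estimates for interactions that pass, does not forbid others, and the CONSORT checklist in SAP Appendix A (item 18) asks for results of any subgroup analyses performed. What can be said is that no separate estimates are planned for the rest.

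Finally, SAP 3.3 asks for caution with secondary analyses, and nothing links a subgroup result to stopping or to the primary conclusion. That limits the harm but leaves the selection rule and the label unchanged.

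**Conclusion.** The point holds as a fault in selective reporting and labelling. With no heterogeneity, the chance that at least one SAP factor passes is 59% for independent tests and 56-57% with TM tied to site under the assumed structure. It drops below half if TM is untestable and continuous time is left out, and is 36% for the Protocol's list.

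It is tempting to read 59% as the probability of a false subgroup claim. The documents do not support that: it is the probability that at least one gate opens and triggers separate estimates, and no passage turns that into a claim that MSU works only in some groups.

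The firmer finding is the size of what gets through. Chance differences that pass average 0.088, larger than the 0.07 the trial is designed to detect. This assumes an even split, 986 evaluable patients and the unadjusted SD of 0.385. An uneven split raises the figure, and covariate adjustment that reduces the residual SD lowers it. The documents do not show that 0.05 is the right level: that choice trades false positives against already low power.

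**What to change.** In SAP 5.1.5 and Protocol 7.F:

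- Report the MSU effect with its 95% CI in every level of every pre-specified subgroup, with the interaction p-value, whatever its size.
- Remove the 0.2 test as the condition for producing estimates.
- State how many interaction tests are done, counting continuous time, and label the subgroup results exploratory.
- If 0.2 is kept, describe it as a sensitive screen chosen because interaction power is low, and do not call a result that passes it significant. No fixed 0.05 rule is needed.

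This extends to subgroups the preference in SAP 5.1.4 for confidence limits over formal tests where power is limited. The cost is revised wording and one forest plot; no new data are needed.

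Showing every subgroup does not control multiplicity. It removes the selection and lets the reader see all the comparisons.
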